12. Use of nefazodone, selective serotonin reuptake inhibitors (SSRIs, such as fluoxetine, sertraline, escitalopram, citalopram, paroxetine), serotonin and norepinephrine reuptake inhibitors (SNRIs, such as desvenlafaxine, duloxetine, venlafaxine), reversible and non-reversible monoamine oxidase inhibitors (such as selegiline, phenelzine, tranylcypromine), tricyclic antidepressants (such as amitriptyline, imipramine, nortriptyline), noradrenergic and specific serotonergic antidepressant (NaSSA) mirtazapine, serotonin modulator and stimulator antidepressants (such as vilazodone or vortioxetine), or the norepinephrine, serotonin and dopamine reuptake inhibitor bupropion within 30 days (90 days for fluoxetine) prior to screening or during the study. **NOTE:** Subjects on stable treatment ( $\geq 30$  days prior to screening) with St. John's Wort may continue this therapy during the study with no expected change in dose.
  13. Treatment with an injectable depot neuroleptic within 90 days prior to screening or during the study.
  14. Subjects who meet the criteria for suicidal intent, plan and/or behavior on the S-STS at screening or Day 1. These criteria are a score of 3 or 4 on questions 2 or 13, or 2 or higher on any of the following questions: 1a (only if 1b is coded YES), 3, 4, 5, 6, 7, 8, 9, 10, 11, 12, or 14.
  15. In the process of litigating for compensation for a psychiatric disorder. Subjects who are in the process of applying for medical or VA benefits and/or those who have settled a disability claim prior to enrollment in the trial are eligible.
  16. History of Huntington's, Parkinson's, and/or Alzheimer's disease, multiple sclerosis, seizures (history of childhood febrile seizures are not exclusionary), epilepsy, or stroke.
  17. History of allergy, sensitivity, or intolerance to N-methyl-D-aspartate receptor (NMDAR) ligands, including ketamine, dextromethorphan, memantine, methadone, dextropropoxyphene, or ketobemidone, as well as current use of such agents.
  18. Received an investigational drug product or device within 30 days (or 5 half-lives, whichever is longer for a drug product) of dosing.
  19. Previously received NYX-783.
  20. Screening QT interval corrected for heart rate (HR) by Fridericia's formula (QTcF)  $>450$  (males) or  $470$  (females) milliseconds (msec) or an ECG that is not suitable for QT measurements (e.g., poorly defined termination of T-wave in the investigator's opinion).

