## **2.2.2. Safety Endpoints**

### **2.2.2.1. Secondary Safety and Tolerability Endpoint(s)**

Safety and tolerability endpoints for this study will be based on: incidences of adverse events (AEs) and any changes in vital signs, physical examination findings (including weight), 12-lead ECG results, clinical laboratory values, and suicidality assessments (Sheehan Suicidality Tracking Scale [STS-S]).

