- Sheehan Suicidality Tracking Scale (S-STS) = The standard version of the S-STS is a 16-item scale that assesses the seriousness of suicidality phenomena on a Likert-type scale (0 to 4) ranging from 0 = “not at all” to 4 = “extremely.” The S-STS score will be derived by data-management. The S-STS accommodates a wide range of timeframes. In clinical trials, the frequently used variants are “in the past week”, “in the past month”, “since the last visit”, “lifetime look back”, and “in the past day.” In this study, during screening, "in the past month" version is used. For all the other visits "since the last visit" version of the S-STS is used.
- Subjects with high S-STS scores- Subjects with a score of 3 or 4 on any questions 2, 3, 4, 5, 6, 7, 8 or 13 in the S-STS questionnaire will be flagged.

- Placebo Non-responder = A Placebo Non-responder must satisfy the following criteria.
  - Randomized to placebo in Stage 1 of the study
  - Week 4 whose CAPS-5 total score reduction from baseline [Day 1]  $\leq 35\%$  and Week 4 CAPS-5 total score is  $\geq 26$
- Change from baseline = value at current visit – value at baseline (as defined in Section 6.1.1).
- TEAE = this is any adverse event with an onset date on or after first dose of study drug through 7 days after last dose of study drug. The Stage in which an event is considered treatment emergent will also be determined based on the relative onset timing against the first dose of Stage-specific study drug. Adverse Events with an onset during the 7 days after end of Stage 2 will be part of Stage 2.
- Duration of reported treatment period (years): For displays of TEAEs, it may be necessary to standardize rates of events due to variable treatment reporting periods. For Stage-specific reporting, durations are computed based on (the date of the last dose of study drug - the date of the first dose of Stage-specific study drug + 1).
- Treatment Related AEs= For each reported AE/SAE, the investigator assesses the relationship to study drug and categorize them into the following categories: Not Related = Unrelated and Unlikely Related, Related = Possibly Related and Probably Related). If an assessment is missing, then it will be treated as Related.
- Sexual Abuse= this is used to flag subjects who were victims of sexual abuse. If the medical history term preferred term is ‘Sexual Abuse’ or ‘Victim of Sexual Abuse’ then those subjects will be flagged as victim of sexual abuse.

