## 9.3. S-STS

Data collected for S-STS will be summarized using descriptive statistics. Change from baseline will also be calculated and summarized in the same manner. All S-STS data will be provided in the data listings.

A summary of subjects with a score of 3 or 4 on questions 2 to 8 and 13 will be presented by stage and treatment group.

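### The SAP's high-score S-STS flag and table omit six items that the protocol's suicidality exclusion uses, even at a score of 3 or 4, so the count by arm can be too low

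*SAP*

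**What the plan says.** SAP 6.1.4 (Derived Variables) creates a flag for high S-STS scores: "Subjects with a score of 3 or 4 on any questions 2, 3, 4, 5, 6, 7, 8 or 13". SAP 9.3 (S-STS) uses the same items and cut-off in its table: "subjects with a score of 3 or 4 on questions 2 to 8 and 13 will be presented by stage and treatment group". The same section plans descriptive statistics, change from baseline and a full listing: "All S-STS data will be provided in the data listings".

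Protocol 8.2, Exclusion 14, applies to "Subjects who meet the criteria for suicidal intent, plan and/or behavior on the S-STS at screening or Day 1". Its first part reads "These criteria are a score of 3 or 4 on questions 2 or 13". Its second part adds a score of "2 or higher on any of the following questions: 1a (only if 1b is coded YES), 3, 4, 5, 6, 7, 8, 9, 10", and the item list runs on to its end as "3, 4, 5, 6, 7, 8, 9, 10, 11, 12, or 14".

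Protocol 14.10.5 asks only for an S-STS summary by dose group and visit and defines no high-score set. SAP 2.2.2.1 names S-STS suicidality among the safety endpoints. SAP 6.1.4, 9.3 and Section 11 (changes from the protocol) give no reason for choosing these eight items.

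**The concern.** A table of subjects with high suicidality scores will be read as counting everyone who scored high on an item that the trial itself treats as serious. The protocol treats 1a (when 1b is YES), 9 to 12 and 14 that way for entry, and there a score of 2 is enough. The SAP leaves the same items out at any score. The list is not a simple range either: Q13 is in, while Q9 to Q12 and Q14 are out, so a reader cannot work out the logic.

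What is at stake is the completeness, by stage and arm, of one descriptive count on a stated safety endpoint. No inferential result depends on it.

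**Working it through.** The plan has no figure of its own to reproduce here. The check compares item sets.

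**Inputs.** Items and cut-offs come from Protocol 8.2 (Exclusion 14), SAP 6.1.4 and SAP 9.3. The item scale of 0 to 4 comes from SAP 6.1.4.

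| Item | Exclusion 14 (screening, Day 1) | SAP 6.1.4 flag and 9.3 table |
|---|---|---|
| 1a (if 1b is YES) | 2 or higher | not used |
| 2 | 3 or 4 | 3 or 4 |
| 3 to 8 | 2 or higher | 3 or 4 |
| 9 to 12 | 2 or higher | not used |
| 13 | 3 or 4 | 3 or 4 |
| 14 | 2 or higher | not used |

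**Items.** Exclusion 14 names 1a and 2 to 14, which is 14 items. The flag names 2 to 8 and 13, which is 8. Omitted: 14 − 8 = 6 (1a, 9, 10, 11, 12, 14). The flag and the table use identical sets.

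**Item-score combinations at 3 or 4.** Exclusion 14: 14 × 2 = 28. Flag: 8 × 2 = 16. Omitted: 28 − 16 = 12, all from the six items (6 × 2 = 12). Every flagged combination also lies inside Exclusion 14, so the flag is a strict subset.

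**When a subject is missed.** Suppose a subject scores 4 on Q10 at Week 6 and no more than 2 on each of Q2 to Q8 and Q13. That subject is not counted. With the same 4 on Q10 and a 3 on Q4, the subject is counted. The undercount therefore arises only when no 3 or 4 falls on Q2 to Q8 or Q13.

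**How many.** This cannot be estimated, because the documents give neither item wording nor item rates.

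**Weight of one subject, for scale only.** With the planned n = 156 and 4:1:1 allocation, Stage 1 has 156 × 4/6 = 104 on placebo and 156/6 = 26 per active arm. One subject is 1/26 = 3.8 percentage points in an active arm and 1/104 = 1.0 in placebo. For Stage 2, assume that the planned 15% Stage 1 dropout is equal across arms. Then 104 × 0.85 = 88.4 are re-randomized 3:2:2, giving 37.9/25.3/25.3, and one subject is 1/25.3 = 4.0 points in an active arm. Any single subject has this weight in any safety table. It does not show that anyone is missed.

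**The case against.** The strongest reply is that the two lists serve different purposes. Exclusion 14 decides who may enter, while the flag describes what happens afterwards, and no passage links them. The SAP does not mirror eligibility limits elsewhere. Exclusion 31 uses 2 × ULN for ALT, AST and GGT, whereas SAP Table 2 uses 3 × ULN and has total rather than direct bilirubin. Exclusion 23 and SAP Table 3 also use different heart-rate limits. No reasons are given there either.

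Suicidality also has other routes into the report. Protocol 12.4.6 has post-baseline suicidality recorded as an adverse event, with no item list or cut-off. SAP 9.2 summarizes suicidality and self-injurious behavior as events of interest for each stage, following the layout by treatment group in 9.1. All S-STS data are listed, and Protocol 13.2 has the DSMB look at change in S-STS suicidality.

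Most of this stands. It rules out three stronger readings that a reader might infer:

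- That the SAP breaches the protocol. It does not. Protocol 14.10.5 sets no high-score rule, and Protocol 14 allows further analyses in the SAP.
- That suicidality on the six items goes unreported. It does not, given the listings and the adverse-event route.
- That a 2 on Q3 to Q8 should have been flagged. Leaving it out fits a label of high, and it is not counted as an error here.

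The reply does not explain why whole items are left out at the scale maximum. A different cut-off for monitoring is ordinary. A table of high scores that cannot register a 4 on six of these items is a different matter. The adverse-event tables depend on an event being identified and coded, and no S-STS score is tied to that step. The 9.3 descriptive statistics might include item frequencies, and the table shells cited in SAP 13 are not supplied. Even so, separate item tables would not give the number of subjects with any high score.

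**Conclusion.** The point holds as a gap in one descriptive safety table. The flag and table cover 8 of the 14 items, and 16 of the 28 item-score combinations at 3 or 4, that Exclusion 14 uses. Followed as written, the table can undercount by stage and arm the subjects with a high S-STS score, and the SAP gives no reason.

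The size in subjects is unknown and may be zero. A reader might infer an actual undercount or an imbalance between arms, but the documents support neither.

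The conclusion rests on two things. The first is that the SAP text is complete on this count, since the shells could not be checked. The second is Exclusion 14's own description of what its items identify, since the item wording is not in the documents. The priority is lower: a cheap improvement to the reporting of a stated safety endpoint.

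**What to change.** In SAP 6.1.4, extend the existing 3-or-4 flag to all 14 items: 1a (only if 1b is coded YES) and Q2 to Q14. In SAP 9.3, tabulate subjects meeting the extended flag by stage and treatment group, and keep the present Q2 to Q8 and Q13 count as a sub-row. If there was a reason for the eight-item list, one sentence in 6.1.4 should give it.

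Two additions are optional: a row using Exclusion 14's lower cut-off of 2, and a Stage 2 row for subjects who first meet the criterion after Week 4. Neither is needed to close this gap.

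The cost is one changed derivation and one extra table row, from S-STS data already collected at Weeks 2, 4, 6 and 8 or early termination. The high-score count may come out slightly larger. The change affects reporting only and alters no subject's management.

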### 9.1. Adverse Events

The number, percentage and incidence rate of subjects reporting treatment emergent AEs (TEAEs), grouped by MedDRA system organ class (SOC) and preferred term (PT) (coded using MedDRA v21.1), will be tabulated by Stage, and treatment group. In the case of multiple occurrences of the same TEAE within the same subject and Stage, a subject will only be counted once for each PT or SOC. Similar methods will be used to provide summaries further reported by severity and relationship. In the summaries reporting severity and relationship to study medication the event with the maximum severity and strongest relationship will be reported, respectively. For these analyses, missing severity and relationship will be imputed as described in Section 6.1.3.2.

The frequency, percentage, and incidence rate of subjects reporting TEAEs, will be reported as described for the following summaries:

- TEAEs by SOC and PT
- TEAEs by SOC, PT, and maximum severity
- Treatment-related TEAEs by SOC and PT
- Treatment-related TEAEs by SOC, PT, and maximum severity

An overall summary of TEAEs, TEAEs leading to discontinuation of study, serious TEAEs, Severe or life-threatening TEAEs, and fatal AEs will be reported. This summary will also be reported for treatment-related TEAEs. Overall summaries for TEAEs and

treatment-related TEAEs by maximum severity will also be provided. The number of total events at each level of TEAE reporting will also be used in the calculation of incidence rate per subject-years of study participation given the specified Stage and reporting treatment period (total events/total patient-years included in the reported treatment period). In general, the duration of the reported treatment period is based on the amount of time a subject has taken the assigned drug within each Stage of reporting for a specified treatment; this is described in more detail in Section 6.1.4.

Missing and partially missing AE start and/or stop dates will be used to determine TEAE status for reporting, according to the specifications described in Section 6.1.5.

In the AE data listings, all AEs will be displayed. AEs that are not treatment-emergent will be flagged.

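### Incidence rates count adverse events for 7 days after the last dose but stop person-time at the last dose, so Stage 2 rates are about 25% too high for a 28-day completer if the event rate is constant

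*SAP*

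**What the plan says.** Two neighbouring definitions in SAP 6.1.4 set the numerator and the denominator of the adverse event rate.

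- **Events.** A TEAE is one that starts "on or after first dose of study drug through 7 days after last dose of study drug". The tail after the second stage is allocated explicitly: "Adverse Events with an onset during the 7 days after end of Stage 2 will be part of Stage 2".
- **Time.** The stage-specific duration is "the date of the last dose of study drug - the date of the first dose of Stage-specific study drug + 1". It has no 7-day extension.

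SAP 9.1 plans incidence rates by stage and treatment group, beside counts and percentages. The rate is "total events/total patient-years included in the reported treatment period", and the period is described as "based on the amount of time a subject has taken the assigned drug within each Stage of reporting". The same section also calls the measure an "incidence rate per subject-years of study participation", which taken alone could include the follow-up week.

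**The concern.** A rate needs events and time at risk from the same window. Here the 7 days after the last dose can add events but never add time. The effect differs by stage. A subject who goes on to Stage 2 starts the new study drug the day after the Week 4 visit (Protocol 10.1), so has essentially no tail in Stage 1. Every Stage 2 subject can have one. The same true event rate would therefore look higher in Stage 2 than in Stage 1 because of the formula alone. SAP 6.1.4 introduces the duration variable in order to standardise rates when reporting periods vary, and this mismatch works against that purpose.

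**Working it through.** The documents state no adverse event rate, so there is no planned figure to reproduce. The check is person-time arithmetic.

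**Inputs from the documents**
- Tail in the TEAE definition: 7 days (SAP 6.1.4).
- Planned Stage 2 dosing: Days 29 to 56, so 56 − 29 + 1 = 28 days (Protocol synopsis, Table 4).
- Window of ±3 days at Weeks 4 and 8: Stage 2 dosing of about 22 to 34 days at the extremes (Protocol Table 4).
- Safety follow-up 7 ± 3 days after therapy (Protocol 9.9).
- Dropout: 15% in Stage 1, 11% in Stage 2 (SAP 3.2).

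**Assumptions, because the documents give no figure**
- The event rate in the tail equals the on-drug rate (r = 1). A range of r is shown below.
- The tail is fully observed unless stated.
- Dropouts stop dosing when they drop out. Their mean dosing time m is 3 days (early), 14.5 days (uniform) or 25 days (late).

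**1. One subject in Stage 2.** Excess = r × tail days / dosing days.

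| Dosing days | Excess at r = 1 |
|---|---|
| 34 | 7/34 = 20.6% |
| 28 | 7/28 = 25.0% |
| 22 | 7/22 = 31.8% |
| 14 | 7/14 = 50% |
| 7 | 7/7 = 100% |

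**2. Sensitivity at 28 dosing days.** With r = 0 the excess is 0%; r = 0.5 gives 12.5%; r = 1.5 gives 37.5%; r = 2 gives 50%. If only 4 tail days are observed at r = 1, it is 4/28 = 14.3%.

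**3. Stage 2 pooled, 11% dropout.** Excess = 7 / (0.89 × 28 + 0.11 × m).
- Late: 7/27.67 = 25.3%.
- Uniform: 7/26.52 = 26.4%.
- Early: 7/25.25 = 27.7%.

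**4. Stage 1 pooled, 15% dropout.** This takes Stage 1 duration to end at the last Stage 1 dose, and only dropouts carry a tail. Excess = 0.15 × 7 / (0.85 × 28 + 0.15 × m).
- Late: 1.05/27.55 = 3.8%.
- Uniform: 1.05/25.98 = 4.0%.
- Early: 1.05/24.25 = 4.3%.

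**5. Stage 2 against Stage 1.** Under uniform dropout, 1.264/1.040 = 1.22. Equal true rates would appear about 20% higher in Stage 2.

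**6. Between arms within a stage.** Suppose 20% on drug and 5% on placebo stop at Day 7. This split is an assumption; the plan gives none by arm.
- Stage 1: drug (0.8 × 28 + 0.2 × 14)/(0.8 × 28 + 0.2 × 7) = 25.2/23.8 = 1.059; placebo 27.3/26.95 = 1.013. The rate ratio shifts by 1.059/1.013 = 1.045.
- Stage 2: drug (0.8 × 35 + 0.2 × 14)/23.8 = 30.8/23.8 = 1.294; placebo 33.95/26.95 = 1.260. The rate ratio shifts by 1.294/1.260 = 1.027.

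**7. Illustration.** Assume 0.5 events per 28 days. The true rate is 0.5/28 × 365.25 = 6.52 per patient-year. The SAP formula gives 6.52 × 35/28 = 8.15. With person-time over the same 35 days it returns to 6.52.

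**The case against.** The strongest reply accepts the mismatch and disputes its importance.

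- **Off-drug events may be rarer.** Protocol section 5 gives a half-life of about 4 hours with minimal accumulation, so little drug remains for most of the tail. The 25% then falls, to 12.5% at half the on-drug rate. This stands, although events that cluster after stopping would push the figure the other way.
- **The tail may not be observed.** Non-serious events are collected only to the last day of participation (Protocol 12.5.3), and subjects who withdraw consent or are lost may contribute little tail. This stands, and it weakens the early-stopper figures most.
- **No between-stage comparison of adverse events is planned, and the protocol asks only for numbers and percentages of subjects** (Protocol 14.10.1). Both are true. However, SAP 9.1 commits to rates by stage, and readers will set the two stages side by side.
- **The reference to study participation is only loose wording.** Largely fair: the same sentence and the next tie the rate to the reported treatment period and to dosing time. It is an ambiguity to tidy, not a second definition.
- **The error overstates rates and does not hide harm.** True for each rate taken alone.

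A reader might infer that 25% is a ceiling. It is not: pooled Stage 2 values reach 27.7% under the plan's own dropout, and shorter dosing within the visit windows gives up to 31.8%. A reader might also infer a material bias between arms. The documents do not support that: even an assumed 20% v 5% split in stopping moves the rate ratio by only 4.5% in Stage 1 and 2.7% in Stage 2.

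**Conclusion.** The defect is real and nothing elsewhere in the SAP corrects it. With a constant event rate and a fully observed tail, the formula overstates the Stage 2 rate by about 25% for a 28-day completer and by about 25% to 28% pooled with 11% dropout, depending on when dropouts stop. Stage 1 is overstated by about 4%, provided its duration ends at the last Stage 1 dose. The duration formula does not say so: it names the last dose of study drug without restricting it to the stage. Taken literally, it would run a continuing subject's Stage 1 time to about 56 days. SAP 9.1 points to the stage-limited reading.

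The distortion falls on absolute rates and on reading Stage 2 against Stage 1. Ratios between arms with similar dosing time are little changed. Counts and percentages do not use this denominator and are unaffected. The plan should correct this, but it does not threaten the planned counts and percentages.

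**What to change.** In SAP 6.1.4 and 9.1, define person-time for TEAE rates over the TEAE window: from the first dose of the stage to the earliest of (a) the last dose in that stage plus 7 days, (b) the first dose of the next stage, or (c) last contact. Divide by 365.25; the variable is labelled in years, but the present formula yields days. Use this denominator for every TEAE rate, and replace the reference to study participation in 9.1 with it. The last-contact limit deals with partly observed tails, and tying the last dose to the stage removes the Stage 1 ambiguity.

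The cost is one changed derivation, with no new data. A completer's Stage 2 rate with a full tail falls by 1 − 28/35 = 20%, whatever the off-drug event rate. The result describes the whole TEAE window and not on-drug time alone, so table footnotes should say so.

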### **7.3. Justification of Dose**

The planned dose levels in this study are NYX-783 50 mg/day and 10 mg/day. Based on the preliminary PK results of the Phase 1, first-in-human study in healthy male and female volunteers (NYX-783-1002), the maximum plasma concentration ( $C_{max}$ ) of NYX-783 50 mg is expected to be approximately 0.8  $\mu\text{g/mL}$ . Total exposure (area under the plasma-concentration curve [ $AUC_{0-24}$ ]) is expected to be approximately 5.0  $\mu\text{g}\cdot\text{h/mL}$ .

In the contextual fear conditioning test, NYX-783, when administered to rats as a single oral dose of 1 mg/kg, facilitated fear extinction learning on extinction Days 1-4 and prevented the

re-consolidation of fear memory when retested on Day 14 compared to vehicle. At this pharmacologically-active dose (1 mg/kg) in rats, the plasma  $C_{max}$  is calculated to be 0.5  $\mu\text{g/mL}$ .

In addition, a single dose of NYX-783 in the fear conditioning stress model provided a long-term effect, preventing freezing behavior after one dose of drug in rodents and preventing recovery of fear after 14 days. One objective of this Phase 2 study is to confirm that the observed preclinical long-lasting effects are translatable to humans, i.e., once daily (QD) administration provides long-lasting benefits.

The pharmacologic effects of NYX-783 are currently believed to be driven primarily by  $C_{max}$ . Thus, the dose planned for the current clinical study is expected to result in human plasma concentrations that are within the  $C_{max}$  range that was associated with positive effects on -fear extinction measures.

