### **3.5. Method of Assigning Subjects to Treatment Groups**

On Day 1, subjects will be randomized to receive placebo, NYX-783 50 mg QD, or NYX-783 10 mg QD in a 4:1:1 ratio, respectively. Placebo responders and placebo non-responders (CAPS-5 total score reduction from baseline  $\leq 35\%$  and total CAPS-5 total score  $\geq 26$  at Week 4) will be identified at the completion of Stage 1 (Weeks 1-4) in a blinded fashion; then, each group (i.e., placebo responders and placebo non-responders) will be re-randomized in a blinded fashion to placebo, NYX-783 50 mg QD, NYX-783 10 mg QD in a 3:2:2 ratio, respectively, for Stage 2 (Weeks 4-8).

treatment. Subjects who received active treatment during Stage 1 will receive placebo in Stage 2.

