## 4. Statistical Analysis and Reporting

### 4.1. Introduction

Data processing, tabulation of descriptive statistics, calculation of inferential statistics, and graphical representations will be performed primarily using SAS (release 9.4 or higher).

Continuous (quantitative) variable summaries will include the number of subjects (n) with non-missing values, mean, standard deviation (SD) (or standard error (SE) if appropriate), median, minimum, and maximum. Confidence intervals (CIs) will be added if appropriate.

Categorical (qualitative) variable summaries will be based on frequencies and percentages.

Unless stated otherwise, efficacy data for endpoints included in mixed effects repeated measures model (MMRM) analyses (groups [1], [2], [3], [7], [8], and [9]) will be summarized by visit and treatment group (Placebo, NYX-783 10 mg QD, NYX-783 50 mg QD) to allow for summary data treatment comparisons as per model inference.

Efficacy data for Stage 2 groups [4], [5], [6], [10], and [11] will be presented separately.

Unless stated otherwise, safety data will be summarized by Stage and treatment group (Placebo [as Placebo Only and Placebo Stage 2, separately], NYX-783 10 mg QD, NYX-783 50 mg QD); data presented by visit will be displayed based on the treatment group which applies at onset for AEs/collection date.

The minimum and maximum will be reported with the same degree of precision (i.e., the same number of decimal places) as the observed data. Measures of location (mean and median) will be reported to 1 degree of precision more than the observed data and measures of spread (SD, SE) will be reported to 2 degrees of precision more than the observed data.

Percentages will be presented to 1 decimal place, unless otherwise specified.

Unless otherwise indicated, all statistical tests will be conducted at a 0.10 significance level using one-sided tests and p-values will be reported. Corresponding 80% CIs (the interpretation of which is equivalent to a one-sided 90% CI when restricted to a single bound) will be presented.

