### **7.3. Demographics and Other Baseline Characteristics**

Demographic and other baseline characteristic data including gender, age, height, weight and BMI will be summarized using descriptive statistics. For the continuous variables, the number of non-missing values and the mean, standard deviation, minimum, median and maximum will be tabulated.

Categorical data for age group, race, sex, ethnicity, family status, education and employment will be summarized by counts and percentages.

Time since start of PTSD (months) will be summarized. Similar descriptive statistics will be used to summarize the baseline clinical measures such as CAPS-5, PCL-5, HADS, CGI-S, PSQI and PSQI-A.

Treatment differences in subject characteristics at baseline (based on Stage 1 treatment groups), will be assessed using Chi-square test (or Fisher's exact test in case Chi-square does not fit the data) for categorical variables and Type III sums of squares analysis of variance (ANOVA) for continuous variables. For continuous variables, in case normality is not assessed a Kruskall-Wallis test will be performed.

These analyses will be performed on both the ITT Population using assigned treatment and SAF Population using actual treatment received for Stage 1 and Stage 2. For SAF Stage 1 analysis, actual treatment received during Stage 1 will be used for treatment group. For SAF Stage 2 analysis, actual treatment received during Stage 2 will be used for treatment group and placebo will be splitted in Placebo Only and Placebo Stage 2.

The number and percentage of subjects reporting types of medical histories will be tabulated by MedDRA system organ class and preferred term (coded using MedDRA v.21.1). This analysis will be conducted by Stage 1 treatment groups for the SAF.

All baseline characteristics data, including medical and disease history, as well as diagnosis information, will be reported in data listings.

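### The specified Stage 2 safety tables put former 50 mg and former 10 mg subjects in one Placebo Stage 2 column, so adverse events after the switch are not summarised by the dose stopped

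*SAP*

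**What the plan says.** - **Stage of an event.** SAP 6.1.4 counts an event as treatment-emergent from the first dose to 7 days after the last dose. Its Stage "will also be determined based on the relative onset timing against the first dose of Stage-specific study drug". The 7-day tail is allotted to a Stage in one place only: "Adverse Events with an onset during the 7 days after end of Stage 2 will be part of Stage 2".
- **Treatment after Stage 1 active drug.** SAP 3.5: "Subjects who received active treatment during Stage 1 will receive placebo in Stage 2". SAP 7.4 starts Stage 2 dosing on the day after the Week 4 visit, so there is no washout.
- **Treatment label.** SAP 5 and 6.1.4 analyse safety by the treatment actually received, determined Stage by Stage. SAP 4.1 adds that "data presented by visit will be displayed based on the treatment group which applies at onset for AEs/collection date".
- **Columns.** SAP 4.1 gives the safety groups as "Placebo [as Placebo Only and Placebo Stage 2, separately], NYX-783 10 mg QD, NYX-783 50 mg QD". SAP 7.3 repeats the division for the Stage 2 safety population: "placebo will be splitted in Placebo Only and Placebo Stage 2". Neither section defines Placebo Stage 2.
- **Reach.** SAP 9 applies the 4.1 groups to the safety data in general, and so to adverse events, S-STS, laboratory and ECG summaries.
- **Contrast with efficacy.** For efficacy, SAP 4.1 names groups 10 and 11 by number and shows them apart from the main comparison groups.
- **Listings.** SAP 9.1 lists every adverse event.

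**The concern.** Subjects leaving 50 mg and subjects leaving 10 mg are the only Stage 2 placebo subjects with prior active exposure. If both sit in one column, a reader of the tables cannot see whether events after stopping differ by the dose stopped.

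This matters because the study's overarching goal begins with safety and tolerability (SAP 2.1). The adverse events of interest in SAP 9.2 include suicidality, dissociative experiences and depression, and its further list includes anxiety and nightmares. For such events it is reasonable to ask what happens after dosing ends. The trial already holds the data by dose, and the column structure discards that split.

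**Working it through.** The plan gives no figure for post-switch events, so there is none to reproduce. The stated power of about 80% plays no part here. The check has two steps.

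**1. Where a post-switch event lands**

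Take a subject randomised to 50 mg who starts Stage 2.
- Onset before the first Stage 2 capsule: Stage 1, shown under 50 mg.
- Onset on or after the first Stage 2 capsule: Stage 2 (SAP 6.1.4), where the treatment received is placebo (SAP 3.5), shown under Placebo Stage 2.

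A 10 mg subject follows the same path into the same column. None of the four column labels carries the Stage 1 dose. Even if Placebo Stage 2 were read as something other than arms 10 and 11, the former doses would still not be separated.

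**2. How many subjects**

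Inputs: 156 subjects and 15% Stage 1 dropout (SAP 3.2); allocation 4:1:1, then 3:2:2 (SAP 3.5). Assumptions: all 156 are in the three current groups and dropout is equal across them.

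- Randomised to each dose: 156 x 1/6 = 26. To placebo: 156 x 4/6 = 104.
- Entering Stage 2 from each dose: 26 x 0.85 = 22.1. Placebo Stage 2 column: 2 x 22.1 = 44.2.
- Placebo subjects re-randomised: 104 x 0.85 = 88.4. Placebo again (arms 4 and 7): 88.4 x 3/7 = 37.9. To each dose: 88.4 x 2/7 = 25.3.
- Subjects per dose who can contribute events after stopping: 22.1 + 25.3 = 47.4. Share without a dose label in the tables: 22.1/47.4 = 47%. The other 53% stop at the end of Stage 2, and their 7-day tail stays with their dose.

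**Illustrations of dilution (assumed counts and rates, not estimates)**

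| Former 50 mg | Former 10 mg | Pooled column |
|---|---|---|
| 4/22 = 18% | 0/22 = 0% | 4/44 = 9% |
| 20% (4.4 of 22) | 5% (1.1 of 22) | 5.5/44 = 12.5% |

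**The case against.** Assigning an event to the treatment in force at onset is a clear and coherent convention, and it should stay. Several stronger readings are tempting, and the documents do not support them.

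- **That post-switch events cannot be tied to a dose at all.** All events are listed, and each can be linked to the Stage 1 dose by subject. Subjects who stop in Stage 1 without a Stage 2 capsule keep the general 7-day window under their own dose. Events with incomplete start dates count in both Stages by default (SAP 6.1.3.1). About 25 subjects per dose supply labelled post-dose events in Stage 2.
- **That these events contaminate the placebo comparator.** Placebo Stage 2 is kept apart from Placebo Only, so an excess after active drug could still show between those two columns. Only the split by former dose is lost.
- **That capture windows are biased.** A completer's window is about 28 days in Stage 1 and 28 + 7 = 35 days in Stage 2. Within each Stage, however, all groups have the same window for completers, and SAP 9.1 plans no comparison of a dose across Stages.
- **That the protocol expects withdrawal effects.** Protocol 7.3 says "a single dose of NYX-783 in the fear conditioning stress model provided a long-term effect", but this concerns fear extinction in rats, that is, efficacy. Protocol 14.4.1 assigns arms 10 and 11 to exploratory efficacy. No rebound reaction is described. With a half-life of about 4 hours (Protocol 7.3), 2^(-24/4) = 1.6% of drug remains at 24 hours, so residual exposure is not the issue after the first day.

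Two further objections stand as limits. The pooling is inferred, because the label is undefined and the table shells cited in SAP 13 are not available here. Split columns are also thin: one subject is 1/22 = 4.5 percentage points, against 1/44 = 2.3 in the pooled column.

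**Conclusion.** The point holds for the safety summaries that the SAP text specifies. Events starting after the switch from Stage 1 active drug appear in one Placebo Stage 2 column, and about 22 former 50 mg and 22 former 10 mg subjects are not shown by the dose they stopped. It is a gap in presentation. It does not bias a planned comparison, remove data or touch the efficacy analysis, and no inferential test of adverse events is described. The counts rest on the planned 156 subjects and 15% dropout. The pooling rests on the natural reading of an undefined label, and the shells could show otherwise. It is worth correcting because safety is the leading aim and the change is cheap.

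**What to change.** 1. In SAP 4.1 and 7.3, define Placebo Stage 2 as subjects on active drug in Stage 1 who take placebo in Stage 2. Split it in the Stage 2 safety tables into former 50 mg (arm 10) and former 10 mg (arm 11). Keep treatment at onset as the primary display, and bring the shells into line.
2. Optionally, add one descriptive table of adverse events with onset in the first 7 days of Stage 2, by Stage 1 dose. Use arms 4 and 7 (placebo in both Stages, about 38 subjects) over the same 7 days as the reference.
3. Do not move those events into the Stage 1 dose columns. That would lengthen the window for arms 2 and 3 while Stage 1 placebo had no matching tail.

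The cost is SAP wording, one extra column and, if wanted, one extra table. That table repeats events already counted in Stage 2 and needs a footnote saying so. The downside is smaller denominators, so the split columns should be read descriptively.
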